#### 9.1.1. Primary Efficacy Analysis and Key Secondary Analyses

[REDACTED]

[REDACTED]

[REDACTED] primary efficacy analysis model, the model efficiency as well as a change in the treatment effect will be increased. Including this factor in the model will also make the results more generalizable to other studies in which the sample characteristics may differ from the current study [2].

In addition, the primary efficacy endpoint [REDACTED]. For this subgroup analyses, observed case data only will be used; that is, missing values will not be imputed.

### 9.1.2. Secondary Efficacy Analyses

Secondary efficacy endpoints are indicated in Section 4.2.2. Secondary efficacy endpoints will be analyzed by study eye, fellow eye, and binocular (if available) using the the PPS1 and PPS2 populations, and the mITT population for selected endpoints (see the list of planned tables, Section 12.1, for details).

All continuous secondary endpoints derived from VA assessments, such as change in DCNVA, DCIVA, and BCDVA, will be analyzed using Early Treatment Diabetic Retinopathy Study (ETDRS) letters correctly read. Any secondary endpoints using Snellen measurements will be converted from letters read as follows:

**Table 3 Snellen Equivalents to VA Assessment Letters Read**

DCNVA/DCIVA letters	Snellen	BCDVA letters
≥75	20/15	≥60
70 - 74	20/20	55 - 59
65 - 69	20/25	50 - 54
60 - 64	20/32	45 - 49
55 - 59	20/40	40 - 44
50 - 54	20/50	35 - 39
45 - 49	20/63	30 - 34
40 - 44	20/80	25 - 29
35 - 39	20/100	20 - 24
30 - 34	20/125	15 - 19
25 - 29	20/160	10 - 14
<25	20/200	<10

Each of the continuous secondary efficacy endpoints will be analyzed using analysis of covariance (ANCOVA), with observed value as the dependent variable, treatment, [REDACTED] respective baseline value included as the covariate. Another ANCOVA will be applied with change from baseline as the dependent variable using the same factors and covariates.

The output from each ANCOVA will include the LSM and SE for all treatment groups, along with each LSM, the 95% CI and associated p-value for Nyxol vs. Placebo for Stage 1 time points, and Nyxol + LDP vs. Nyxol + LDP vehicle, Placebo + LDP, and Placebo + LDP vehicle for Stage 2 time points. [REDACTED]

For each of the secondary endpoints related to percent of subjects achieving certain criteria, the analysis will be performed using a logistic regression model with treatment and light/dark irides as factors, and the respective baseline as a covariate. For each analysis, the percentage

of subjects in each treatment group meeting the criteria will be presented, and the OR with 95% CI and p-value will be provided for Nyxol vs. Placebo for Stage 1 time points, and Nyxol + LDP vs. Nyxol + LDP vehicle, Placebo + LDP, and Placebo + LDP vehicle for Stage 2 time points. Categorical pupil diameter endpoints will be assessed using the study eye, fellow eye, and either eye, which is defined as achieving a given criterion in either eye.

In addition, each secondary efficacy endpoint will be [REDACTED].

Finally, select questions from the Subject Questionnaire will be analyzed. The results for Question 1 (change in near vision) and Question 5 (satisfaction with near vision) will be analyzed at Visit 2 (Stage 1 Day 8) and Visit 5 (Stage 2 Day 8) using an ANCOVA model with numeric observed response as the dependent variable ([REDACTED] and treatment as a factor. Only observed subject questionnaire data will be used; no imputation will be performed for missing data.

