#### 5.1. Primary And Secondary Endpoints

#### **Efficacy:**

The primary efficacy endpoint is the percent of subjects with  $\geq 15$  letters of improvement in photopic binocular DCNVA and with < 5 letters of loss in photopic binocular BCDVA at 30 min post-LDP/vehicle comparing Nyxol + LDP to placebo + LDP vehicle at Visit 5 (Stage 2 Day 8).

This comparison will be analyzed first using a hierarchical testing method.

09/29/2023 Page 25 of 76

Measurements:

- Best-corrected distance VA will be measured in photopic conditions by a high-contrast Standard Early Treatment Diabetic Retinopathy Study (ETDRS) illuminated chart (on wall or stand) at 4 m
- Distance-corrected intermediate VA will be measured by a highcontrast Near Visual Acuity Chart in the Precision Vision Small 914 Illuminator Cabinet (light box) at 26 inches (66 cm)
- Distance-corrected near VA will be measured in by a high-contrast Near Visual Acuity Chart in the Precision Vision Small 914 Illuminator Cabinet (light box) at 16 inches (~40 cm) (Appendix 2)

All of the efficacy endpoints will be analyzed overall and by light/dark irides at all timepoints. Subjects will also be analyzed by binocular, study eye, and fellow eye, where applicable.

In photopic lighting conditions, the the distance and near illuminated charts will be at a

The subject will be in the same room for all assessments, and every effort will be made to have the same person perform the measurements at all visits.

For VA, measurements will be made in letters and will be converted to LogMAR and lines, as appropriate.

All efficacy endpoints will also be analyzed by the Modified Intention-to-Treat (mITT) Population and selected efficacy endpoints will be analyzed using the PP Population as specified in the Statistical Analysis Plan (SAP).

09/29/2023 Page 26 of 76

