## **APPENDIX 2: VISUAL ACUITY CHARTS**

DCNVA will be measured using the Near Visual Acuity Chart (logarithmic Visual Acuity Chart 2000, chart #1 and #2) in the Precision Vision Small 914 Illuminator Cabinet (light box) at 16 inches (~40 cm) (letters recorded, later converted to LogMAR and number of lines).

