#### Near High-Contrast Chart

BCDVA will be measured with a Standard ETDRS illuminated 100% high-contrast chart (on wall or stand) at 4 m.

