#### **Distance High-Contrast Chart**

## **APPENDIX 3: ADRENERGIC AND CHOLINERGIC DRUGS**

The following drugs are examples of drugs which cannot be used within 7 days prior to Screening or during the study unless the drug, dose, and regimen has been consistent for the 7 days prior to Screening; *however, tamsulosin is specifically excluded*. *This list is not inclusive of all drugs in these classes. If there is any doubt, please consult with the Medical Monitor.* 

Alpha-1-agonists	Non-selective alpha-	Direct-acting	Gastrointestinal
Methyl	antagonists	acetylcholine receptor	Atropine
norepinephrine	Phenoxybenzamine	agonists	Belladonna
Naphazoline	Tolazoline	Choline esters	Denadonna
Oxymetazoline	Labetalol	Acetylcholine	Parkinsonism
Tetrahydrozoline	Carvedilol	Bethanechol	Amantadine
	Trazodone	Carbachol	
Phenylephrine	Phentolamine		Benztropine
Xylometazoline	Phentolamine	Methacholine	Biperiden Triberrahen i det
Metaraminol			Trihexyphenidyl
Methoxamine	Alpha-1-antagonists	Plant alkaloids	
Midodrine	Alfuzosin	Arecoline	Antimuscarinic
Amidephrine	Prazosin	Nicotine	agents
	Doxazosin	Muscarine	Antipsychotics
Alpha-2-agonists	Tamsulosin	Pilocarpine	(clozapine,
Brimonidine	Terazosin		quetiapine)
Clonidine	Silodosin	Indirect-acting	Atropine
Guanfacine	Fuzosin	acetylcholine receptor	Benztropine
Guanabenz		agonists	Biperiden
Guanoxabenz	Alpha-2-antagonists	Reversible	Chlorpheniramine
Guanethidine	Atipamezole	cholinesterase inhibitors	
Xylazine	Idazoxan	Donepezil	Certain SSRIs
Tizanidine	Yohimbine	Edrophonium	(Paroxetine)
Methyldopa	Raulscine	Neostigmine	Dicyclomine
Norepinephrine	Mirtazapine	Physostigmine	(Dicycloverine)
Lofexidine		Pyridostigmine	Dimenhydrinate
Medetomidine		Rivastigmine	Diphenhydramine
		Tacrine	Doxepin
Undetermined		Caffeine	Doxylamine
alpha agonists		Huperzine A	Flavoxate
Ergotamine		1	Glycopyrrolate
Etilefrine		Irreversible	Glycopyrronium
Indanidine		cholinesterase inhibitors	Hyoscyamine
Mephentermine		Echothiophate	Ipratropium
Metaraminol		Isoflurophate	Orphenadrine
Methoxamine		Malathion	Oxitropium
			Oxybutynin
		Acetylcholine receptor	Promethazine
		antagonists	Propantheline
		Scopolamine	bromide

Dicycloverine	Scopolamine
Tolterodine	Solifenacin
Oxybutynin	Tolterodine
Ipratropium	Tiotropium
Mamba Toxin (MT 7 )	-
Pirenzepine	Tricyclic
Telenzepine	antidepressants
_	Trihexyphenidyl
Antivertigo	Tropicamide
Meclizine	Umeclidinium
Scopolamine	
_	Antinicotinic agents
	Bupropion
	Dextromethorphan
	Doxacurium

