#### 4.2.2. Secondary Endpoints

##### Efficacy:

[Redacted text block containing multiple paragraphs of efficacy data, all obscured by black bars.]

[REDACTED]

Measurements:

- Best-corrected distance VA measured [REDACTED]
- Distance-corrected intermediate VA [REDACTED]
- Distance-corrected near VA [REDACTED]
- Pupil diameter [REDACTED]

All of the efficacy endpoints will be analyzed overall and by light/dark irides at all timepoints. Subjects will also be analyzed by binocular, study eye, and fellow eye, where applicable.

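### SAP Table 3 converts near (~40 cm) and intermediate (66 cm) letters to Snellen with one column; with the same near chart at both distances, as the visible text reads, Snellen-based DCIVA is labelled about two rows too poor

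*SAP*

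**What the plan says.** - **Protocol 5.1, Measurements.** DCIVA is measured with a high-contrast "Near Visual Acuity Chart in the Precision Vision Small 914 Illuminator Cabinet (light box) at 26 inches (66 cm"; DCNVA with a high-contrast "Near Visual Acuity Chart in the Precision Vision Small 914 Illuminator Cabinet (light box) at 16 inches (~40 cm". In the visible words only the distance differs.
- **Protocol 5.1, lighting sentence.** It is cut short, but the visible part names two kinds of chart: "the distance and near illuminated charts will be at a".
- **Protocol Appendix 2.** "DCNVA will be measured using the Near Visual Acuity Chart (logarithmic Visual Acuity Chart 2000, chart #1 and #2", in the same light box at about 40 cm. The visible chart headings are "Near High-Contrast Chart" and "Distance High-Contrast Chart". Letters are recorded and later converted to LogMAR and lines; no correction for distance is visible.
- **SAP 4.2.2, Measurements.** The line that begins "Distance-corrected intermediate VA" is redacted after those words.
- **SAP 9.1.2 and Table 3.** Continuous acuity endpoints, DCIVA among them, are analysed in letters. Any secondary endpoint on the Snellen scale is converted through Table 3, which has one column headed "DCNVA/DCIVA letters" and a separate one only for best-corrected distance acuity (BCDVA).

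**The concern.** Snellen and logMAR values are visual angles. The same printed letter subtends a smaller angle at 66 cm than at 40 cm, so reading it at 66 cm shows better acuity. One letters-to-Snellen column can therefore serve two distances only if the chart at each distance is scaled for that distance. Table 3 gives BCDVA its own column but puts near and intermediate acuity together, although the visible protocol text describes one kind of chart for both.

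At stake is the labelling of any Snellen-based DCIVA result. SAP 9.1.2 analyses percent-achieving endpoints by logistic regression. A misplaced cut-off there would change which subjects count as responders and what the reported percentage means.

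**Working it through.** **Inputs.** Table 3, near/intermediate column: 70 letters is the lower bound for 20/20, with 5 letters per row. Distances from Protocol 5.1: 66 cm and ~40 cm, or 26 and 16 inches. Assumption: the near chart is scaled for 40 cm. Appendix 2 supports this by tying the chart to that distance but does not state a design distance.

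**Step 1: reproduce the column.** From 20/20 to 20/200 is 1.0 logMAR in ten rows, so a row is 0.1 logMAR and a letter is 0.02. With 70 letters at logMAR 0, the rule is logMAR = 1.40 − 0.02 × letters, and the Snellen denominator is 20 × 10^logMAR.

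| Lower bound (letters) | Denominator by formula | Table 3 |
|---|---|---|
| 75 | 15.9 | 15 |
| 70 | 20.0 | 20 |
| 65 | 25.2 | 25 |
| 60 | 31.7 | 32 |
| 55 | 39.9 | 40 |
| 50 | 50.2 | 50 |
| 45 | 63.2 | 63 |
| 40 | 79.6 | 80 |
| 35 | 100.2 | 100 |
| 30 | 126.2 | 125 |
| 25 | 158.9 | 160 |
| 20 (open row, <25) | 200.0 | 200 |

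Eleven of the twelve rows agree to about 1% or better; the open top row is nominal. The column is consistent for a chart read at its design distance.

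**Step 2: effect of distance.** For one chart moved from 40 to 66 cm:
- log10(66/40) = log10(1.65) = 0.2175 logMAR; 0.2175 / 0.02 = 10.9 letters, or 2.2 rows.
- log10(26/16) = log10(1.625) = 0.2109 logMAR; 0.2109 / 0.02 = 10.5 letters, or 2.1 rows.

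So for a 40 cm chart read at 66 cm, DCIVA logMAR = 1.40 − 0.02 × letters − log10(66/40).

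**Step 3: example.** At 55 letters, Table 3 gives 20/40. At 66 cm:
- Using centimetres: 1.40 − 1.10 − 0.2175 = 0.0825, and 20 × 10^0.0825 = 24.2.
- Using inches: 1.40 − 1.10 − 0.2109 = 0.0891, and 20 × 10^0.0891 = 24.6.

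That is about 20/24 to 20/25.

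**Step 4: corrected bounds.**
- 20/40: 55 − 10.87 = 44.13 (inches: 55 − 10.54 = 44.46), so 45 whole letters.
- 20/20: 70 − 10.87 = 59.13 (inches: 70 − 10.54 = 59.46), so 60 whole letters.

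Rows are 5 letters apart, so every whole-letter lower bound falls by 10, for either pair of distances.

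**Step 5: rows of error.** Against the corrected bounds, the present label is two rows too poor for 20 to 69 letters, one row too poor for 15 to 19 and 70 to 74, and unchanged below 15 and from 75 up, where the open end rows absorb the shift.

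**The case against.** The strongest objection is that the geometry is sound but the premise is not proved. An error needs one physical chart at both distances. Protocol 5.1 may be naming a type of chart; the specific model in Appendix 2 is tied to DCNVA only, and the visible DCIVA bullet does not refer to that appendix. The lighting sentence is truncated, the chart images are absent, and the DCIVA line in SAP 4.2.2 is redacted. A chart scaled for 66 cm, or a letter correction before conversion, could stand in the hidden text, and hidden text is not an omission. Nor does any visible endpoint report DCIVA in Snellen terms; the Table 3 heading is the only sign of one.

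Most of this stands, and it is why the point is conditional and rated low. It does not remove the point. The identical chart description in Protocol 5.1 is positive text, not silence, and SAP 9.1.2 makes the shared column the operative rule for any Snellen output.

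A reader might go further and infer that the near-acuity labels are wrong instead, with the chart scaled for 66 cm and DCNVA labelled too well. No visible text supports that: Appendix 2 ties the named chart to about 40 cm for DCNVA, so the DCNVA conversion can be taken as it is. A reader might also infer that the primary result is at risk. It is not, because that endpoint counts letters gained and lost and does not pass through Table 3.

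**Conclusion.** The point holds as a conditional one of low severity. On the natural reading of Protocol 5.1 and Appendix 2, the shared Table 3 column labels Snellen-based DCIVA about two rows too poor, with an offset of 0.211 to 0.217 logMAR. The DCIVA cut-off for 20/40 would be 55 letters where 45 is enough, so a result reported as 20/40 or better would really mean about 20/25 or better.

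This rests on two assumptions that the documents support but do not prove: that the near chart is scaled for 40 cm, and that the same chart is read at 66 cm without correction. Only Snellen-based DCIVA secondary outputs would be affected. Whether any is planned is not visible, and the share of subjects concerned cannot be worked out from the documents. The same cut-off applies to every arm, so the mislabelling is not directed at any one of them. The primary endpoint, letter scores and changes in letters are unaffected.

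**What to change.** 1. Confirm which chart is used for DCIVA and its design distance, and state both in Protocol 5.1 or Appendix 2.
2. If it is a separate chart scaled for 66 cm, name it and keep the shared column after checking that its letter ranges match.
3. Otherwise, give DCIVA its own Table 3 column from logMAR = 1.40 − 0.02 × letters − log10(66/40):

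| Snellen | DCIVA letters |
|---|---|
| 20/15 | ≥65 |
| 20/20 | 60–64 |
| 20/25 | 55–59 |
| 20/32 | 50–54 |
| 20/40 | 45–49 |
| 20/50 | 40–44 |
| 20/63 | 35–39 |
| 20/80 | 30–34 |
| 20/100 | 25–29 |
| 20/125 | 20–24 |
| 20/160 | 15–19 |
| 20/200 | <15 |

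4. If no Snellen-based DCIVA output is planned, removing DCIVA from the column heading is enough.

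The cost is one confirmation and, at most, one table column and one derivation line; no new data are needed. SAP 3.1 has the plan finalised before unmasking, and the change belongs before that point.

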## **10. SAFETY ANALYSES**

All safety analyses will be conducted using the SP unless specified otherwise below. All safety analyses will be completed using the actual treatment a subject received. Observed case data will be used; no imputation will be performed for missing safety data except for the limited situations described in Section 7.3.2.

All safety data will be presented in by-subject listings. Unscheduled assessments will not be summarized but will be included in the listings.

### **10.1. Adverse Events**

AEs will be coded using MedDRA, Version 25.1.

Treatment-emergent adverse events (TEAEs) are defined as any AE that begins or worsens after initiation of the investigational product and through the subject's last study visit (study completion or early termination).

If the onset of an AE is on or after the date of first dose of study medication or is increasing in severity after first dose of study medication, then the AE will be considered treatment emergent.

Only TEAEs will be summarized; all AEs (TEAE, non-TEAE) will be included in a by-subject listing.

TEAEs that start during Stage 1 will only be counted in the Stage 1 tables using the Treatment 1 that was actually taken, regardless of the TEAE stop date. TEAEs that start during Stage 2 will be counted in both Stage 1 and Stage 2 tables.

The number and percent of subjects with any TEAEs will be summarized by SOC and PT by treatment group and overall. At each level of tabulation (e.g., at the PT level), subjects will be counted only once if they had more than one such event reported during the AE collection period.

Note that in MedDRA, ocular events are coded to the SOC of "Eye Disorders". Thus, using SOC in the summaries will provide a separation of ocular and non-ocular adverse events.

The following summary tables will be presented for TEAE data:

- Overall summary of TEAEs (completed for both the SP and mITT population)
- Summary table of TEAEs by SOC and PT
- Summary table of TEAEs by SOC, PT, and by greatest relationship level to study drug (not related, unlikely related, possibly related, probably related, definitely related, or unknown)
- Summary table of TEAEs by SOC, PT, and maximum severity (mild, moderate, severe)

- Summary table of serious TEAEs by SOC and PT
- Summary table of TEAEs leading to withdrawal from the study by SOC and PT
  
- Summary table of TEAEs leading to study medication discontinuation by SOC and PT

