Primary Efficacy Endpoint	The primary efficacy endpoint is the percent of subjects with $\geq 15$ letters of improvement in photopic binocular DCNVA and with < 5 letters of loss in photopic binocular BCDVA at 30 min post-LDP/vehicle comparing Nyxol + LDP to placebo + LDP vehicle at Visit 5 (Stage 2 Day 8). This comparison will be analyzed first using a hierarchical testing method.
Key Secondary Efficacy Endpoints	
Other Secondary Efficacy Endpoints	

09/29/2023 Page 11 of 76

	All efficacy endpoints will be analyzed overall and by light/dark irides. Separate analyses will be performed for binocular, study eye, and fellow eye, where applicable. All efficacy endpoints will also be analyzed by the Modified Intention-to-Treat (mITT) Population. Selected analyses will be performed on the Per Protocol (PP) Population as specified in the Statistical Analysis Plan (SAP).
Safety Endpoints	Safety measures are adverse events, ocular tolerability, IOP, BCDVA, biomicroscopy, ophthalmoscopy, HR and BP, and subject questionnaire. Urine pregnancy tests for females of childbearing potential will be conducted.
Study Medications, Dose, and Mode of Administration	Treatment 1:         • Nyxol ® Eye Drops (Phentolamine Ophthalmic Solution 0.75%), or         • Placebo (ie, Nyxol vehicle)         Treatment 1 is dosed during both Stages 1 and 2 of the study and is taken daily in the evenings near bedtime, except during the Washout Period.         Treatment 2:         • LDP (Pilocarpine Hydrochloride Ophthalmic Solution 0.4%), or         • LDP vehicle         Treatment 2 is dosed during Stage 2 of the study and is taken daily in the mornings.

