# 5. STUDY DESIGN

This is a randomized, double-masked, placebo-controlled, multicenter, Phase 3 study in approximately 320 subjects with presbyopia. The study will be performed in 2 stages, as shown in Appendix 4.

Subjects will be randomized 1:1:1:1 to treatments for both stages at Visit 1 (Screening/Baseline). Treatment 1 assignment in Stage 1 will be maintained for Stage 2. Stage 1 will consist of 2 treatment groups (Nyxol or placebo [ie, Nyxol vehicle]), with approximately 160 subjects in each group. Stage 2 consists of 4 treatment groups (Nyxol + LDP, Nyxol + LDP vehicle, placebo + LDP, and placebo + LDP vehicle), with approximately 80 subjects per treatment group.

In Stage 1, the safety and efficacy of Nyxol as a single agent will be evaluated over the following 1 day and 7 days of daily dosing in the evenings near bedtime, except the evening before Visit 2, when Treatment 1 is dosed as close to 12 hours prior to Time 0 min for that visit. Following Visit 2 (Stage 1 Day 8), subjects will discontinue dosing Treatment 1 for 7 to 14 days (Washout Period). During the Washout Period, subjects will return for Visit 3 (Stage 1 Day  $10 \pm 1$  day) to assess the resolution of drug treatment effects.

During Stage 1, subjects will dose with Treatment 1 (Nyxol or placebo [ie, Nyxol vehicle]) in the evenings near bedtime (except for Visit 1 [Stage 1 Day 1], when the subject is dosed during the day at the study site).

Measurements will be made at multiple visits and timepoints, and analysis will consist of comparison across the 2 arms:

- Nyxol
- Placebo

# Stage 2: Dosing of Treatments 1 and 2

Visit 4 (Stage 2 Day 1) is the start of Stage 2. In Stage 2, the efficacy and safety of Nyxol + LDP will be evaluated following 1 day and 7 days of dosing, in which Treatment 1 (Nyxol or placebo) is dosed daily in the evenings near bedtime, except the evening before Visits 4 and 5, when Treatment 1 is dosed as close to 12 hours prior to the scheduled time for those visits. Treatment 2 (LDP or LDP vehicle) is dosed daily in the mornings. Treatment 2 will be dosed at the study site at the beginning of Visits 4 and 5 (Stage 2 Days 1 and 8, respectively).

Measurements will be made at multiple visits and timepoints, and analysis will consist of comparison across the 4 arms:

- Nyxol + LDP
- Nyxol + LDP vehicle
- Placebo + LDP
- Placebo + LDP vehicle

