## 5. STUDY METHODS

### 5.1. General Study Design and Plan

This is a randomized, double-masked, placebo-controlled, multicenter, Phase 3 study in approximately 320 subjects with presbyopia. The study is performed in 2 stages, as described below.

Subjects are randomized 1:1:1:1 to treatments for both stages at Visit 1 (Screening/Baseline). Note that Visit 1 (Screening/Baseline) assessments are recommended to be performed on the same day; however, in instances in which subjects are unable to complete the full day of assessments for Visit 1, subjects may be scheduled to return for the completion of Visit 1 within 1 week of Screening. If Visit 1 is split over 2 separate days, all visit assessments up to and including randomization must occur on the first day, and then the subject should return to complete their post-randomization assessments on the second day.

Stage 1 consists of 2 treatment groups (Nyxol or placebo [ie, Nyxol vehicle]), with approximately 160 subjects in each group. Stage 2 consists of 4 treatment groups (Nyxol + LDP, Nyxol + LDP vehicle, placebo + LDP, and placebo + LDP vehicle), with approximately 80 subjects per treatment group. Treatment assignments for Stage 1 and Stage 2 are assigned at randomization prior to Stage 1.

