## **7.4. Planned Study Analyses**

### **7.4.1. Statistical Summaries: Descriptive and Inferential**

Categories for data presentation and analysis will consist of each treatment group: Nyxol and placebo for Stage 1, and Nyxol + LDP, Nyxol + LDP vehicle, Placebo + LDP, and Placebo + LDP vehicle for Stage 2.

All statistical tests will be two-sided and a difference resulting in a p-value of less than or equal to 0.05 will be considered statistically significant. The p-values for the analysis of secondary efficacy endpoints and safety endpoints will be considered descriptive, unless the endpoint is used for the hierarchical testing method. All p-values will be rounded to and displayed in four decimals. If a p-value less than 0.0001 occurs, it will be shown in tables as <0.0001.

Descriptive summaries of variables will be provided where appropriate. For continuous variables, the number of non-missing values (n), mean, standard deviation, median, minimum, and maximum will be tabulated by treatment group. For categorical variables, the counts and proportions of each value will be tabulated by treatment group. Expansion of descriptive table categories within each treatment may occur if such elaborations are thought to be useful.

All study-related data collected will be presented in listings. Study-related data not subject to analysis according to this plan will not appear in any tables or graphs but will be included in the data listings.

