## **8. SUMMARY OF STUDY DATA**

### **8.1. Subject Disposition**

A summary of the analysis sets includes the number and percentage of subjects by Stage 1 treatment group and overall for the following categories: subjects in the ARP, subjects in the SP, subjects in the mITT Population, and subjects in the PP Population. All percentages will be based on the number of subjects in the ARP. A similar summary will be presented by Stage 2 treatment group.

End of trial information will also be summarized in these tables, including the number of subjects completing the study, the number of subjects who prematurely discontinued the study with reasons for withdrawal, the number of subjects completing the study medication dosing, and the number of subjects who prematurely discontinued the study medication with reasons for study medication discontinuation.

A by-subject data listing of study completion information including the reason for premature study withdrawal, if applicable, will be presented.

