#### **8.5. Prior and Concomitant Medications**

The number and percentages of all concomitant medications will be summarized by Stage 1 treatment group, Anatomical Therapeutic Chemical (ATC) level 4, and PT. The total number of concomitant medications and the number and percentages of subjects with at least 1 concomitant medication will be summarized by Stage 1 treatment group. A similar summary will be presented by Stage 2 treatment group. All summaries will be performed using the SP.

A concomitant medication is defined as any medication taken on or after the day of first exposure to study drug.

Prior medications are defined as any medication that has a start and stop date prior to the day of first exposure to any study drug, collected from up to 30 days prior to Screening. The total number of prior medications and the number and percentages of subjects with at least 1 prior medication will be summarized by Stage 1 treatment group, Stage 2 treatment group, and overall.

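### SAP 10.1 counts Stage 2-onset adverse events in the Stage 1 tables, so those tables show whole-study incidence by Treatment 1, not single-agent Stage 1 incidence

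*SAP*

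**What the plan says.** SAP 10.1 has two adjacent counting rules. A TEAE with onset in Stage 1 goes into the Stage 1 tables only, under the Treatment 1 actually taken. For later onsets, "TEAEs that start during Stage 2 will be counted in both Stage 1 and Stage 2 tables". Within each level of tabulation, "subjects will be counted only once if they had more than one such event reported during the AE collection period", and that period is not cut at the end of Stage 1. The TEAE window runs from first dose to last study visit.

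SAP 7.4.1 gives the table columns as "Nyxol and placebo for Stage 1" and the four combinations for Stage 2. Protocol 5 states the purpose of the first stage: "In Stage 1, the safety and efficacy of Nyxol as a single agent will be evaluated". LDP or its vehicle is Treatment 2, and according to the protocol synopsis "Treatment 2 is dosed during Stage 2 of the study and is taken daily in the mornings". SAP 5.1 plans about 160 subjects per Stage 1 group and four Stage 2 groups, "with approximately 80 subjects per treatment group".

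Protocol 10.3.6 asks for TEAEs by treatment group and gives no rule by stage.

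**The concern.** A reader of a Stage 1 table with a Nyxol and a placebo column will take the percentages as event rates before anyone received LDP. Under SAP 10.1 they are not. A term first reported on LDP in Stage 2 enters the Stage 1 placebo column, or the Stage 1 Nyxol column, as if it had arisen on that treatment alone. The columns also cover a second course of Treatment 1.

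Elsewhere the SAP keeps the stages apart. SAP 9.1.2 (secondary efficacy) and SAP 10.3 (ocular tolerability) compare Nyxol with placebo at Stage 1 time points and the four groups at Stage 2 time points. A reader would expect the adverse event tables to follow the same pattern. At stake is the readable summary of safety in the single-agent stage, which is a stated purpose of Stage 1.

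**Working it through.** The plan attaches no figure to this rule, so there is none to reproduce. The check is what the rule counts, and then what it does to a percentage.

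1. **Content of the two table sets (SAP 10.1).** Stage 1 tables = Stage 1 onsets + Stage 2 onsets = all TEAEs. Stage 2 tables = Stage 2 onsets only. No set holds Stage 1 onsets only.

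2. **Share of each Stage 1 column given LDP later (SAP 5.1).** 80/160 = one half, in the Nyxol column and in the placebo column alike.

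3. **Effect per subject on an any-event percentage** (overall, or for one system organ class or preferred term). A subject whose first such event starts in Stage 2 adds 1/160 = 0.625 points; ten such subjects add 6.25 points. These percentages cannot fall, because the rule only adds events.

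4. **Maximum-severity and greatest-relationship tables.** A single category can move either way. A subject with a mild event in Stage 1 and a moderate event of the same term in Stage 2 leaves the mild category (-0.625 points) and enters the moderate one (+0.625 points).

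5. **An event caused only by LDP.** Assume it occurs in a fraction r of LDP-treated subjects in Stage 2 and never otherwise. Each column gains r × 80/160 = r/2. At r = 10%, that is 8 of 160 subjects, or 5 points, in each column, although nobody was on LDP in Stage 1.

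6. **Illustration with the Phase 2 (VEGA-1) rates in protocol 3.2.** The reported counts and percentages imply 15/44 for Nyxol + LDP, 6/30 for Nyxol, 6/31 for placebo + LDP and 2/45 for placebo; 44 + 30 + 31 + 45 = 150, the stated study size. Assume that each rate applies in each stage. The mean Stage 2 rate is then (0.3409 + 0.2000)/2 = 0.2705 in the Nyxol column and (0.1935 + 0.0444)/2 = 0.1190 in the placebo column. The column percentage depends on how far the same subjects have events in both stages:

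| Overlap between stages | Nyxol column | Placebo column | Difference |
|---|---|---|---|
| Stage 1 onset only | 20.0% | 4.4% | 15.6 |
| Same subjects (nested) | 27.0% | 11.9% | 15.1 |
| Independent | 1 - 0.8000 × 0.7295 = 41.6% | 1 - 0.9556 × 0.8810 = 15.8% | 25.8 |
| Different subjects (disjoint) | 20.0 + 27.0 = 47.0% | 4.4 + 11.9 = 16.3% | 30.7 |

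Both columns rise in every case. The difference between them falls slightly in one case and rises in the other two, so the rule does not fix its direction.

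**The case against.** The strongest reply is that whole-study tables by Treatment 1 are what the SAP intends. It uses the Stage 1 treatment group as a grouping variable for data that are not limited to Stage 1. In SAP 8.1, where subjects are grouped that way, "End of trial information will also be summarized in these tables". In SAP 8.5, also tabulated by Stage 1 treatment group, "A concomitant medication is defined as any medication taken on or after the day of first exposure to study drug", with no end at Stage 1. The counting rule in SAP 10.1 is stated openly, the protocol requires no Stage 1-onset table, and the table titles are redacted. This stands as a possible explanation. It does not cure the rule: SAP 10.1 speaks of Stage 1 tables, does not state this intent, and lists no summary limited to Stage 1 onset.

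A second reply also stands and limits the consequence. The Stage 2 tables show the two LDP-vehicle groups separately, so LDP-free rates for Nyxol and placebo can be read there for Stage 2. By-subject listings allow Stage 1 incidence to be rebuilt. SAP 7.4.1 makes safety p-values descriptive.

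Three stronger readings are tempting but not supported:

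- *The Nyxol-placebo comparison is biased in a known direction.* LDP is allocated equally to both columns, and the direction of any change in the difference is not determined.
- *The VEGA-1 figures measure or bound the effect.* They come from a 7-day, two-visit study and are imprecise (exact 95% intervals 0.5% to 15.1% for 2/45 and 7.7% to 38.6% for 6/30), and the overlap between stages is unknown.
- *The SAP leaves the start of Stage 2 undefined.* SAP 5.1 and protocol 5 set it at Visit 4. What is unclear is the evening before, when Treatment 1 restarts; protocol 3.5 includes that dose in Stage 2 dosing. Protocol 9.3 lists a start date for an event and no start time, and the case report form is not available. Under the current rule this affects only the Stage 2 tables.

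**Conclusion.** The point holds as a fault in a descriptive tabulation rule. Followed exactly, SAP 10.1 yields Stage 1 tables that show whole-study TEAE incidence by Treatment 1, with about half of each column exposed to LDP during part of the period counted. The readable plan has no table of TEAE incidence by Stage 1 onset. There is no directional bias, no lost data and no effect on any efficacy analysis.

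The size is unknown. The documents support only the per-subject step of 0.625 points for any-event percentages, assuming the planned 160 subjects per column. The conclusion rests on the readable text; a Stage 1-onset table in the redacted list would leave only the naming to correct. The change should be made because safety on Nyxol as a single agent is a stated purpose of Stage 1 and the correction is cheap.

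**What to change.** In SAP 10.1, replace the two counting rules with wording such as: *Stage 1 TEAE tables count TEAEs with onset from the first Treatment 1 dose up to the start of Stage 2, by Treatment 1 actually taken. TEAEs with later onset are counted in the Stage 2 tables, by the four treatment groups.*

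State one cut-off for this purpose, for example the first study-drug dose after the washout, and add one sentence assigning events dated on the evening before Visit 4. If the whole-study summary by Treatment 1 is wanted, keep it under the title *Entire study*. If that summary was always the intent, retitle it and add the Stage 1-onset set.

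The cost is a few SAP sentences and an onset filter in programming, with no new data collection. If the whole-study set is kept, there is one additional set of TEAE tables, and SAP 10.1 lists seven table types per set. A few events with a date but no time will be placed in a stage by convention.
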